allocation ratio using stratified, restricted randomization. PWID and MSM-focused ICCs were initiated in 11 intervention sites in June 2014. Venues (non-governmental organizations [NGOs] or government facilities) were selected for scale-up following discussions between the Indian government, NGO leaders, community members, and investigators. In the PWID stratum of this trial, ICCs were scaled from existing opioid agonist treatment (OAT) centers to incorporate other risk reduction services including syringe services programs (SSP) and HIV counseling and testing (HCT). Some medical services at these ICCs are provided on-site including sexually transmitted infection (STI) treatment while others are provided through peer navigated referral (e.g., tuberculosis treatment, antiretroviral therapy [ART]).

After 2 years, a second (post-intervention) RDS was conducted in all 22 sites from October 2016 and May 2017. ICCs resulted in significant improvements in HIV testing, but limited ART uptake.²⁸ In response, we launched a second phase to evaluate supplementing ICCs with demand-side incentives for HIV care (DA041034; ClinicalTrials.gov identifier: NCT02969915). Of the prior sites,

16 were selected based on HIV prevalence and poor care engagement (8 PWID, 8 MSM). ICCs have been scaled in all cities with half randomized to receive incentives for HIV care. A third cross-sectional sample will be accrued in late 2020 to evaluate community impact of the incentives. This protocol will take place in 7 of the 8 PWID ICCs in this ongoing trial (**Figure 7.1.1**). One of the 8 sites is being excluded due to low HCV prevalence.

7.1.4. High burden of HCV among PWID in India but poor engagement across the HCV care continuum

In the 2013 baseline assessment for the aforementioned trial, 14,481 PWID were recruited in 15 cities (~1000 per city) across India.²⁹ HCV prevalence ranged from 4.9 – 64.9% in the 15 cities.³⁰ Only 1,272 (7%) had ever been tested for HCV and the most common reason for not having been tested was never having heard of HCV (51%)

followed by low risk perception. Of 5,777 PWID with evidence of HCV infection, only 5.6% were aware of their HCV positive status. In 2016, at the evaluation survey, HCV prevalence ranged from 37.2 to 76.6% in the 7 proposed sites (**Figure 7.1**).

[figure not shown]

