12.2.4. SVR evaluations

SVR evaluations will be assessed on the majority of participants at week 24 (12 weeks after treatment completion). For a minority of participants who receive 24 weeks of treatment, the SVR evaluations will take place at week 36. The window for the SVR assessment visit will be -2 weeks (10 weeks after treatment completion) to 60 weeks after treatment completion (i.e., study weeks 22-72). Visits outside this window are allowed with documentation of reason for early/late visit.

If a participant misses the visit window, every attempt should be made to contact participant and complete the SVR evaluation and other evaluations through the end of the study follow-up period.

At this visit, the following assessments will be done in all arms

- Scan biometric to confirm identity
- Administer a brief survey on substance use, risk behavior and quality of life
- Update medication history
- Provide updated contact/locator information
- EHR review, clinical exam, and vital signs
- Draw blood for HCV RNA testing
- Abstract HIV RNA information from government ART book (if HIV infected)
- Pregnancy test (if female)
- Schedule next appointment

The post-SVR evaluations will be scheduled in relation to when participants complete the SVR evaluations.

While COVID-19 safety precautions are in place, in order to reduce face-to-face contact, we will administer surveys, update medication history and collect locator information over the phone. Participants will have to come to the ICC for a brief exam and blood draw (and pregnancy test as needed). Exceptions will be made for this in-person requirement in cases where 1) COVID-19 precautions make travel to the site challenging; and 2) participants are in rehabilitation facilities or cannot travel to the site for another reason.

In cases where the HCV RNA ≥30 IU/ml and <1000 IU/ml, a repeat sample will be drawn ≥14 days after the initial sample as long as it is within the SVR window (i.e., up to 60 weeks after treatment completion)

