12.3.2. Documentation of HIV status and antiretroviral therapy regimen

Clients in the ICCs are offered HIV testing every 6 months. These HIV results are maintained in the EHR. In addition, all HIV positive participants who visit a government ART center receive an ART book which maintains a record of all laboratory testing that is done within government ART centers (i.e., CD4 cell count and HIV RNA) and all ART prescriptions and refills including the name of the medications, the number of pills dispensed and the dose. All of this information is abstracted monthly by ICC staff into the EHR. Using this EHR, HIV status, most recent CD4 cell count, HIV RNA level and ART refill will be documented in the screening eCRF. In cases where no HIV test has been done or the most recent HIV antibody test was negative and completed more than three months prior, an HIV antibody test will be required for screening purposes.

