If a CD4 within 90 days prior to screening is not available in the EHR, a CD4 count will be obtained from an approved local laboratory (HIV-positive participants).

12.3.9.9. Virologic studies.

HCV RNA testing

Screening HCV RNA and SVR HCV RNA testing will be conducted at the YRGCARE Infectious Disease Laboratory in Chennai, India, which is a DAIDS-certified laboratory.

Samples for HCV RNA testing will be processed and shipped as described in Section 12.3.9.11.

Any sample with HCV RNA between 30 – 1000 IU/ml will require resampling for confirmation in a second sample drawn ≥14 days after the initial sample.

HIV RNA testing

HIV RNA testing is generally done at government ART centers. Available HIV RNA results will be abstracted from the ICC EHR.

HCV Core Antigen testing.

For post-SVR visits, re-infection will be assessed using the Abbott ARCHITECT HCV Ag assay. This testing will be conducted at the YRGCARE Infectious Disease Laboratory in Chennai, India.

Samples for HCV Core Antigen testing will be processed and shipped as described in **Section 12.3.9.11**.

12.3.9.10. Stored plasma/serum. Stored plasma and serum will be collected at the indicated visits for future HCV/HIV studies and shipped to the central YRGCARE Infectious Disease Laboratory.

Stored specimens may be used for HCV genotyping/sequencing needed to differentiate between relapse and reinfection among participants failing to achieve SVR. We will also test for the presence of resistance-associated substitutions (RASs) in these specimens by sequencing the nonstructural protein 5A (NS5A) and nonstructural protein 5B (NS5B) regions.

12.3.9.11. Specimen preparation, handling and shipping. All staff handling laboratory specimens will undergo training in Good Clinical Laboratory Practices (GCLP). Additional training certification and recertification will be provided by the Central YRGCARE team in India. The YRGCARE lab is a DAIDS certified laboratory. Certification of the personnel and the procedures on specimen collection, preparation, handling, storage and shipping will be required before sites start collecting and shipping specimens.

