Annual assessments of HIV viral load among HIV/HCV coinfected participants in the 7 ICCs are expected as part of other ICC activities and standard of care at Indian government ART centers. All available viral load measurements for HIV/HCV co-infected PWID enrolled in the trial will be used. Viral suppression will be defined as HIV RNA less than LLOQ. We will compare viral suppression across two groups defined by primary outcome status, which will be cured vs. not cured using logistic regression with generalized estimating equations (GEE) to account for repeated measures within individuals. Because these groups will be defined by the primary outcome and no longer balanced by randomization, analysis will be adjusted for confounding factors including demographics, substance use, needle sharing, MOUD, SSP use, social support and frequency of visits to the ICC. Analyses will be combined across all groups but we will include a covariate for the classification of risk of treatment failure (minimal or elevated) and intervention received. In order to account for missing data due to loss-to-follow-up, we will use inverse-weighting methods.^{4,5}

2d.1. Sensitivity analyses. We will vary the threshold for HIV viral suppression (<150 copies/ml vs. 400 copies/ml vs. 1000 copies/ml) and will also incorporate the revised definition of SVR vs. treatment failure using sequence data.

3. Exploratory analysis

3a. Impact of interventions on medication for opioid use disorder (MOUD) utilization. Daily MOUD utilization data is available in the electronic health record. We will explore the impact of the interventions within strata by arm on new MOUD initiation and MOUD retention using methods of survival analysis, logistic regression with GEE and growth mixture models. Analyses will be adjusted for site. Additional sensitivity analyses will be similar to those reported in the primary and secondary outcome analyses and will include accounting for the prognostic score.

3b. Impact of interventions on quality of life.

Quality of life data is captured at the SVR visit and at semi-annual post-treatment follow-up visits. Using logistic and linear regression with GEE, we will explore the impact of interventions within strata on quality of life after treatment.

3c. Impact of interventions on mortality.

Using Poisson regression, we will explore the impact of interventions within strata on all-cause mortality.

3d. Effect of delays in treatment completion on SVR.

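### SAP 2d scores HIV suppression only where a routine viral load exists, so co-infected participants who attend trial visits but are out of ART care are often left out, and no missing-data rule covers them

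*SAP*

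**What the plan says.** Protocol 8.2 (objective 4) and 7.3 (hypothesis 5) concern all HIV/HCV co-infected participants. SAP 2d compares suppression between cured and not-cured participants by logistic GEE. On the data it says "All available viral load measurements for HIV/HCV co-infected PWID enrolled in the trial will be used". Roughly annual viral loads "are expected as part of other ICC activities and standard of care at Indian government ART centers". Protocol 15.7.2.2 says the same.

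On where results come from, Protocol 12.3.9.9 states: "HIV RNA testing is generally done at government ART centers. Available HIV RNA results will be abstracted from the ICC EHR". Protocol Table 12.1 has no HIV RNA row. At the SVR visit (12.2.4) and the post-SVR visits (12.2.5), the only HIV RNA procedure is abstraction from the government ART book. On who holds that book, 12.3.2 says "all HIV positive participants who visit a government ART center receive an ART book which maintains a record of all laboratory testing".

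The only missing-data provision in SAP 2d is: "In order to account for missing data due to loss-to-follow-up, we will use inverse-weighting methods". The listed adjustment factors (demographics, substance use, needle sharing, MOUD, SSP use, social support, ICC visit frequency) plus risk stratum and intervention do not include ART status. SAP 2d.1 varies only the suppression threshold and the SVR definition.

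**The concern.** Being out of ART care makes a participant both less likely to be suppressed and less likely to have a viral load on file. Such a participant can attend every trial visit. He is then not lost to follow-up, yet he contributes nothing to SAP 2d.

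Two things are at stake. First, the suppression level would describe people in ART care rather than all co-infected participants. Second, the cured versus not-cured comparison would be distorted if ART engagement differs by cure status. The plan itself makes such a difference plausible:

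- Protocol 15.5 uses early ART refills and HIV suppression as the surrogate for HCV treatment failure, which presumes that the two go together.
- SAP 2d forms its groups from primary outcome status, and SAP 1 counts a missing SVR result as failure. The not-cured group may therefore contain more disengaged people.

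**Working it through.** The documents state no rate, sample size or power for HIV suppression, so there is no figure to reproduce. The check traces the data path and then illustrates its effect.

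**Step 1: data path.** Eligibility (Protocol 10.1) does not require ART. No HIV RNA test is scheduled (Table 12.1). Abstraction relies on the ART book, which is given to those who visit an ART centre (12.3.2). Other routes exist: SAP 2d names other ICC activities, Protocol 10.1.3 allows co-enrolment in the ICC+ study, and someone who stopped ART keeps earlier results. Exclusion is therefore frequent rather than certain, and depends on how often off-ART people are tested elsewhere.

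**Step 2: missing-data rule.** The weights are specified for loss to follow-up, and an attending but untested participant is not lost. Even with wider weights, a group with almost no chance of a result cannot be recovered by up-weighting others. SAP 1 scores SVR missing through loss to follow-up or death as failure; SAP 2d has no scoring rule.

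**Step 3: effect on the level.** All inputs are assumptions: a = share in ART care; s = 0.85 suppressed in care; s0 = 0.02 suppressed off ART; t = 0.9 with a viral load if in care; q = share of off-ART people with a viral load.

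- All co-infected: a·s + (1−a)·s0
- As analysed: [a·t·s + (1−a)·q·s0] / [a·t + (1−a)·q]

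| a | All co-infected | Analysed, q=0 | q=0.2 | q=0.5 | q=0.9 |
|---|---|---|---|---|---|
| 0.5 | 43.5% | 85.0% | 69.9% | 55.4% | 43.5% |
| 0.7 | 60.1% | 85.0% | 77.8% | 69.0% | 60.1% |
| 0.9 | 76.7% | 85.0% | 83.0% | 80.2% | 76.7% |

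The gap closes only when off-ART people are tested as often as those in care (q = t).

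**Step 4: effect on the crude cured versus not-cured odds ratio.** The inputs are the same, with equal suppression once in care.

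| ART care, cured vs not cured | All co-infected | Analysed, q=0 | q=0.2 | q=0.5 | q=0.9 |
|---|---|---|---|---|---|
| 70% vs 70% | 1.00 | 1.00 | 1.00 | 1.00 | 1.00 |
| 80% vs 60% | 2.01 | 1.00 | 1.44 | 1.78 | 2.01 |
| 90% vs 50% | 4.28 | 1.00 | 2.10 | 3.26 | 4.28 |

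Worked case, 80% vs 60%:

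- All co-infected: 0.8×0.85 + 0.2×0.02 = 0.684 and 0.6×0.85 + 0.4×0.02 = 0.518. OR = (0.684/0.316)/(0.518/0.482) = 2.01.
- Analysed at q = 0.2: 0.6128/0.76 = 0.806 and 0.4606/0.62 = 0.743. OR = 1.44.

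**Step 5: dependence on the set-up.** The 1.00 at q=0 follows from assuming equal suppression in care. Suppose instead 85% vs 75% suppressed on ART, none suppressed or tested off ART, and ART care of 80% vs 60%.

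- Analysed OR = (0.85/0.15)/(0.75/0.25) = 1.89.
- All co-infected OR = (0.68/0.32)/(0.45/0.55) = 2.60.
- On the log scale this is 0.64 of 0.96, so about two thirds of the association remains.

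**The case against.** **Off-ART people are not wholly excluded.** This stands. Because of the other routes in Step 1, a reader should not infer that everyone off ART disappears from the analysis; the q=0 column is the extreme case.

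**The loss of the association is not general.** This also stands. A reader might infer that the plan removes most of the cured versus not-cured difference. Step 5 shows a case where two thirds remains, and with equal ART care nothing is lost.

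**The crude odds ratio is not the right target.** This is the strongest point, and it stands. The objective is the effect of cure. If people who fail HCV treatment were already out of ART care, the crude difference partly reflects prior engagement. The 2.01 is therefore a descriptive benchmark, not the true effect of cure, and it ignores the planned adjustment. Scoring off-ART people as not suppressed without adjusting for baseline ART status could turn prior disengagement into an apparent benefit of cure.

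**Low ART uptake is not shown for this trial.** Protocol 7.1.3 reports that "ICCs resulted in significant improvements in HIV testing, but limited ART uptake", but this comes from the 2016–17 survey of an earlier 22-site trial in PWID and MSM. Incentives for HIV care followed in half of the later cities, and Protocol 11.1.1.3 describes on-site ART or peer help with refills. A reader might infer that being out of ART care is common here; the documents give no figure.

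**The endpoint is the last of four secondary objectives, a non-randomised comparison, and separate from the primary analysis.** True. This limits the importance of the gap but does not close it.

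**Conclusion.** The gap is real. SAP 2d tends to estimate suppression among people in ART care, while its objective names all co-infected participants, and neither the weights nor SAP 2d.1 addresses attending participants with no viral load. Provided that people out of ART care are tested less often and are less often suppressed, the level is overstated. The comparison is distorted if ART engagement differs by cure status.

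Size and direction for this trial cannot be derived, because the number co-infected, ART coverage and viral-load completeness are not given. Under the assumed 80% vs 60% ART care, the crude 2.01 appears as 1.00, 1.44 or 1.78 when 0%, 20% or 50% of off-ART people have a result; with equal ART care there is no distortion of the odds ratio. As the plan stands, either a null or a positive result for hypothesis 5 would be hard to interpret for the stated population. The primary analysis is unaffected.

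**What to change.** Amend SAP 2d as follows:

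1. Report viral-load availability by cure group and ART status.
2. Add baseline (pre-HCV-treatment) ART status to the adjustment model. Include ART refill status in the inverse weights, and extend the weights to participants in ART care who have no result.
3. Alongside the available-only analysis, pre-specify one that scores a participant as not suppressed in an annual window with no HIV RNA and no ART refill in the EHR, or with ART never started. Adjust it for baseline ART status, and exclude periods such as imprisonment (Protocol 18.2.2) when refills may go unrecorded. Annual windows match the expected frequency of viral loads.

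The cost is SAP wording and some programming. Protocol 12.3.2 already has ART refills abstracted monthly into the EHR and recorded at screening, so no new visit or test is needed. The downside is that people obtaining ART outside the recorded system would be misclassified in analysis 3, which is one reason to keep the available-only analysis beside it.

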15.3.2. Secondary objectives / hypotheses

15.3.2.1. To evaluate whether the intensity of treatment adherence support affects HCV treatment completion rates.

Hypothesis: Among PWID at elevated risk for treatment failure, PWID receiving the high intensity intervention will have significantly higher treatment completion than those receiving either the medium or the low intensity interventions.

Hypothesis: Among PWID at minimal risk for treatment failure, PWID receiving either the high or the medium intensity intervention will have significantly higher treatment completion than those receiving the low intensity interventions.

15.3.2.2. To evaluate whether the intensity of treatment adherence support affects HCV treatment adherence.

Hypothesis: Among PWID at elevated risk for treatment failure, PWID receiving the high intensity intervention will have significantly higher adherence than those receiving either the medium or the low intensity interventions.

Hypothesis: Among PWID at minimal risk of treatment failure, PWID receiving either the high or the medium intensity intervention will have significantly higher adherence than those receiving the low intensity intervention.

15.3.2.3. To estimate the incidence and correlates of HCV reinfection among HCV mono- and HIV/HCV coinfected PWID who achieve HCV cure.

Hypothesis: HCV reinfection will be lower among clients who have higher attendance at OAT programs.

15.3.2.4. To evaluate the impact of HCV cure on HIV viral suppression among HIV/HCV coinfected PWID.

Hypothesis: Among HIV/HCV co-infected PWID, HIV viral suppression will be higher after achievement of HCV cure.

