15.6 Participant Enrollment and Follow-up

We anticipate enrolling 3,000 (approximately 420 per site) persons over a period of 18-24 months with an average of 15-20 participants per site per month. After enrollment, participants will be followed while they are on treatment (for 12 or 24 weeks) through to an SVR evaluation visit 10 – 60 weeks after treatment completion. This will be the minimum amount of follow-up for all those enrolled. Following this, those who achieve SVR and those who are HIV/HCV co-infected (regardless of SVR) will have semi-annual visits thereafter to monitor reinfection. Follow-up will be complete at the SVR evaluation visit for those who do not achieve SVR and are not HIV/HCV coinfected. The maximum follow-up post the SVR evaluation visit for those who achieve SVR is 30 months for a total follow-up of 36 months. The goal will be that everyone who achieves SVR has at least one semi-annual visit after the SVR evaluation visit but it is possible that some individuals who are enrolled late do not have any post SVR follow-up.

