STATISTICAL ANALYSIS PLAN

A precision randomized trial to evaluate the impact of tailored hepatitis C virus (HCV) treatment adherence support on HCV treatment outcomes in HIV/HCV co-infected and HCV mono-infected people who inject drugs (PWID) in India

NCT04652804

Supporting Treatment Outcomes among PWID (The STOP-C Study)	
	-
	Funded by:
	onal Institute of Allergy nfectious Diseases
R01-Al-145555-01 Industry Support Provided by:	
Protocol Chair/Co-Chair:	[name] MPH, Co-Chair [name] [name] MPH, Co- Chair
DAIDS-ES Document Number:	DAIDS-ES ID 38666
Version Number:	1.0
Version Day Month Year:	5 January 2024

SIGNATURE PAGE

I agree to conduct the analysis in accordance with the relevant, current protocol.

I agree to personally conduct or supervise the analysis.

Co-Principal Investigator: [name] MPH / Professor

Signed:

Date: 1/5/24

Co-Principal Investigator: [name], PHD MPH / Professor

Signed: Date: 1/5/24

1. Primary outcome

The primary outcome is sustained virologic response (SVR) defined as HCV RNA < lower limit of quantification (LLOQ) 10 – 60 weeks after completion of treatment (cure). The primary analysis will be intention to treat and will be stratified by the risk of treatment failure (minimal and elevated).

The primary analysis will compare the proportion achieving SVR across level of support (low, medium, high intensity) within the two strata of risk (minimal and elevated) independently. Using log-binomial models (or their extensions, i.e., Poisson regression with robust variance estimation) including adjustment for site as a fixed effect, in the elevated risk stratum, we will compare the proportion achieving SVR in those who received the low and moderate intensity interventions (in separate models) to those who received the high intensity intervention resulting in a relative risk (RR). Analysis will be repeated for the minimal risk stratum except comparing those who receive the high and moderate intensity interventions to the low intensity intervention.

Primary comparisons will be intention to treat. That is, the study population for this analysis will include everyone who was randomized. Individuals with missing data on the outcome of interest either due to loss-to-follow-up or death will be treated as failures.

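### SAP 2d takes cure status from the primary outcome, so co-infected participants with no SVR result would be analysed as not cured in the HIV-suppression comparison

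*SAP*

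**What the plan says.** The hypothesis (protocol 15.3.2.4; hypothesis 5 in protocol 7.3) is "Among HIV/HCV co-infected PWID, HIV viral suppression will be higher after achievement of HCV cure". To test it, SAP 2d and protocol 15.7.2.2 fit a logistic GEE model to HIV suppression. The exposure is set as follows: "We will compare viral suppression across two groups defined by primary outcome status, which will be cured vs. not cured".

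The primary outcome carries one missing-data rule, in SAP 1 and protocol 15.7.2.1: "Individuals with missing data on the outcome of interest either due to loss-to-follow-up or death will be treated as failures".

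The HIV RNA data do not depend on the SVR assessment:
- SAP 2d: "All available viral load measurements for HIV/HCV co-infected PWID enrolled in the trial will be used".
- Protocol 12.3.9: "Available HIV RNA results will be abstracted from the ICC EHR". The tests are generally done at government ART centres.
- Protocol 12.3.2, on ART-book data that include HIV RNA: "All of this information is abstracted monthly by ICC staff into the EHR".
- Protocol 15.6: "those who achieve SVR and those who are HIV/HCV co-infected (regardless of SVR) will have semi-annual visits thereafter".

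SAP 2d acknowledges that the two groups are not randomized. It adjusts for "demographics, substance use, needle sharing, MOUD, SSP use, social support and frequency of visits to the ICC", for risk stratum and for intervention received, and it plans inverse weighting for loss to follow-up. Sensitivity analysis 2d.1 varies the HIV RNA threshold and substitutes a sequence-based SVR definition. Nothing in 2d or 2d.1 limits the analysis to participants with a measured HCV RNA or varies the handling of a missing SVR.

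**The concern.** Counting missing as failure is a familiar convention for comparing randomized arms. Here the same variable becomes an exposure that is meant to describe a biological state. A co-infected participant who took every dose, cleared the virus and then missed the SVR visit would be labelled not cured, while his HIV RNA results continued to enter the model under that label.

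The mislabelling need not be neutral. Missing the SVR visit and having unsuppressed HIV can both follow from weak engagement with care. If so, the not-cured group would show lower suppression even where cure has no effect.

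The planned safeguards do not reach the label. Inverse weighting deals with data that are missing, and a person scored as a failure has no missing exposure. Adjusting for frequency of ICC visits may reduce confounding by engagement, but it cannot make an unknown cure status known. At stake is the answer to a prespecified, directional secondary hypothesis. The primary outcome is not affected.

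**Working it through.** The plan gives no missing-SVR rate, no number of co-infected participants and no power for this analysis, so there is no stated figure to reproduce. The check asks what the not-cured group would contain.

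**Inputs**
- S, the SVR with missing counted as failure. Protocol Table 15.4.1 uses 80–95%. The worked examples in protocol 15.4 use 85% (low/medium support, elevated risk) and 95% (low support, minimal risk).
- c, the cure rate among those tested. Protocol 7.1.1 cites more than 95% for sofosbuvir/velpatasvir. I use 95%, with 97% and 90% as assumptions on either side.
- Pooled S. SAP 2d combines strata and arms. With equal strata and no arm effects, (85% + 95%)/2 = 90%. With the detectable relative risks from the same examples:
  - elevated risk: 0.5 × 0.85 + 0.5 × 0.85 × 1.06 = 0.876;
  - minimal risk: 0.5 × 0.95 + (1/3) × 0.95 × 1.03 + (1/6) × 0.95 × 1.04 = 0.966;
  - mean: about 92%.

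  Both pooled values are assumptions. The documents do not say how co-infected participants divide between strata.

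**Step 1: share of the not-cured group without a result**

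Tested share = S/c. Missing share m = 1 − S/c. Missing share of the not-cured group = m/(1 − S).

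Example, S = 90% and c = 95%: 0.90/0.95 = 0.947; m = 0.053; 0.053/0.10 = 53%.

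| S | c = 90% | c = 95% | c = 97% |
|---|---|---|---|
| 80% | 56% | 79% | 88% |
| 85% | 37% | 70% | 82% |
| 90% | 0% | 53% | 72% |
| 95% | not possible | 0% | 41% |

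At S = 92% the share is about 39% (c = 95%) to 64% (c = 97%).

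**Step 2: when unmeasured people are the majority**

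They reach half when m = (1 − m)(1 − c), that is m = (1 − c)/(2 − c). This gives 9.1% missing at c = 90%, 4.8% at c = 95% and 2.9% at c = 97%.

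**Step 3: direction and possible size if cure has no effect**

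Take c = 95% and m = 10%. Measured failures are 0.90 × 0.05 = 0.045. Let w be the number of HIV RNA results per unmeasured person relative to a measured one. Suppression is assumed to be 80% in measured people, and 60% or 70% in unmeasured people. The unadjusted odds ratio is odds(0.80) divided by the odds in the mixed not-cured group.

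Example, w = 1 and 60%: (0.045 × 0.80 + 0.10 × 0.60)/0.145 = 0.662; odds 1.96; 4/1.96 = 2.04.

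| w | 80% vs 60% | 80% vs 70% |
|---|---|---|
| 1 | 2.04 | 1.47 |
| 0.5 | 1.76 | 1.35 |
| 0.25 | 1.49 | 1.23 |
| 0 | 1.00 | 1.00 |

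**Step 4: with cure defined by measurement**

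Unmeasured people leave the not-cured group and, in the null scenario of Step 3, the odds ratio returns to 1.00. At S = 85% and c = 95%, the not-cured group falls from 15% of co-infected participants to 0.895 × 0.05 = about 4.5%.

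**The case against.** **The carry-over is an inference.** The endpoint itself is a laboratory definition, and the missing-as-failure sentence stands in the paragraph on intention-to-treat primary comparisons. SAP 2d never says that the rule applies there. This is fair. But 2d points to primary outcome status, offers no other definition and sets no restriction to measured participants, so the plain reading stands until the SAP says otherwise.

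**The composition is unknown.** A reader might infer that the not-cured group consists mainly of people lost to care, so that the comparison measures retention rather than cure. The documents do not support that. They give no missing-SVR rate, and the share falls below half in plausible cells (37% at S = 85% with c = 90%; 0–41% at S = 95%). The 85% example also describes only part of a pooled analysis. The group would include deaths and people who missed only the SVR visit while remaining in ART care. Protocol 12.2.4 allows a window of 10 to 60 weeks and continued attempts afterwards, and co-infected participants are followed regardless of SVR, so missingness may be low.

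**The bias may be small.** A reader might also infer a spurious odds ratio of about 3. With 80% versus 50% suppression, S = 85% and equal numbers of viral loads, the unadjusted value is 2.8 (c = 95%) to 3.2 (c = 97%). That is an illustrative upper scenario and does not estimate the planned model. It ignores the adjustment set, and it assumes that people out of care supply as many HIV RNA results as people in care. Step 3 shows how quickly the figure falls when they do not.

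**Later reinfection.** Someone who becomes core-antigen positive after SVR stays in the cured group. Fixing exposure at SVR is a legitimate choice for a hypothesis about suppression after cure, and removing later viral loads would condition on a post-exposure event. I do not count this as an error.

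What remains after these objections is the mislabelling itself, which none of them removes.

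**Conclusion.** The concern holds in a limited form. As written, SAP 2d and protocol 15.7.2.2 code unknown cure status as not cured while keeping those participants' HIV RNA in the model. Cure is therefore misclassified, and the comparison may be confounded by retention. The direction favours the hypothesis only if participants without an SVR result are less often HIV-suppressed and still contribute results.

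The size cannot be fixed from the documents. With pooled SVR of 90% and 95–97% cure among those tested (both assumptions), 53–72% of the not-cured group would be unmeasured by head count; the range is 70–82% at SVR 85% and 0–41% at SVR 95%. The effect on the adjusted odds ratio is not established. This is one observational secondary analysis, and the change is worth making because it is cheap. Whether the same problem affects SAP 3d or the correlates analysis in SAP 1e has not been shown here.

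**What to change.** In SAP 2d and protocol 15.7.2.2:
1. Define cured as measured HCV RNA below the LLOQ at the SVR evaluation, and not cured as measured HCV RNA at or above it.
2. Treat participants without a result, including those who died before it, as having missing exposure. Use either a weighting model for having an SVR result or multiple imputation, a method already planned in SAP 1b. The existing weights for loss to follow-up do not serve this purpose. The imputation model in SAP 1b uses only treatment completion and adherence; for 2d it should also include HIV suppression and the 2d covariates.
3. Report missing-as-failure only as a sensitivity analysis, and tabulate how many in each co-infected group had a measured HCV RNA.
4. Optionally, add a sensitivity analysis with time-varying handling of core-antigen-positive reinfection.

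No new data are needed. The cost is a revised definition, one additional weighting or imputation model, and lower precision: the not-cured group would be about 4.5% of co-infected participants instead of 15% at SVR 85% and 95% cure among those tested, with a wider confidence interval.
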